10.13.8 Progression-Free Survival (PFS and iPFS)

- Per RECIST (v1.1): A PFS time is defined as the time from the first day of study treatment until the first date of radiological disease progression (PD) or death.

- Per iRECIST: An iPFS time is defined as the time from the first day of study treatment until the first date of confirmed disease progression or death. The date of disease progression would be the date of the first iUPD that is confirmed by a later iCPD. This can occur on the subsequent assessment or after a series of persistent iUPD assessments. The date of iUPD will also be used as disease progression if the iUPD assessment is followed by:
 - if the patient stops protocol treatment because they were judged to be clinically unstable, or
 - no further tumor assessments are done, or
 - if the next timepoint responses are all iUPD, and iCPD never occurs, or
 - if the patient dies from their cancer.

An iUPD assessment followed by subsequent non-PD assessments will not be considered as the start of progression. Stopping protocol treatment due to clinical instability is identified as subjects discontinuing from SOT101 with reason 'clinical progression'.

- Per PCWG3-modified RECIST 1.1: PFS time is defined as the time from the first day of study treatment until the date of PCWG3-modified RECIST 1.1 defined confirmed disease progression or death.

Clinical deterioration alone will not be considered as documented disease progression. Only tumor assessments performed before the start of any new anti-cancer treatment (including radiation therapy to the tumor lesion (s)) will be considered in the assessment of PFS/iPFS.

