#### **10.2.6 Resolution of iUPD**

Progression is considered not confirmed, and the overall response becomes iSD/iPR/iCR, if:

- none of the progression-confirming factors identified above occurs, AND
- the target lesion sum of diameters (initial target lesions) is not above the initial disease progression threshold.

The response is classified as iSD or iPR (depending on the sum of diameters of the target lesions), or iCR if all lesions resolve.

In this case, the initial iUPD is considered to be pseudoprogression, and the level of suspicion for progression is “reset”. This means that the next visit that shows radiographic progression, whenever it occurs, is again classified as iUPD by iRECIST, and the confirmation process is repeated before a response of iCPD can be assigned.

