Step 2: iBOR of iPR If an iBOR of iPR is not determined, Step 3 will be performed.	At least two consecutive determinations of iPR or iCR, more than 4 weeks apart, or if not consecutive, with no other assessment between the two determinations other than NE, iCR, iPR.
Step 3: iBOR of iSD If an iBOR of iSD is not determined, Step 4 will be performed.	At least one iSD assessment (or better), ≥ 6 weeks (≥ 42 days) after start of study treatment; if not, at least one follow-up scan (i.e., consecutive scan) evaluated as iSD (or better) is required to determine an iBOR of iSD. If not consecutive scans, with no other assessment between the two determinations other than NE, iCR, iPR, iSD.
Step 4: iBOR of iCPD If an iBOR of iCPD is not determined, Step 5 will be performed.	At least one (i.e., any) iCPD after baseline.
Step 5: iBOR of iUPD If an iBOR of iUPD is not determined, Step 6 will be performed.	At least one (i.e., any) iUPD after baseline.
Step 6: iBOR of NED If an iBOR of NED is not determined, Step 7 will be performed.	If no measurable disease at baseline and all subsequent assessments will be NED.
Step 7: iBOR of NE	Measurable disease at baseline, but not all or any target lesions have been evaluated, or if derivation of iBOR from Step 1 to 6 does not apply.

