10.13.6 Duration of Response (DOR and iDOR)

- Per RECIST (v1.1): Duration of response is defined as the time from first documentation of overall response leading to a confirmed CR or PR until the time of first documentation of overall response of disease progression (PD) or death.
- Per iRECIST: Duration of response is defined as the time from first documentation of overall response leading to a confirmed iCR or iPR until the time of disease progression or death. The date of disease progression will be the first instance of iUPD that is confirmed by a later iCPD, this can occur on the subsequent assessment or after a series of persistent iUPD assessments. The date of iUPD will also be used as disease progression if the iUPD assessment is followed by:
 - if the patient stops protocol treatment because they were judged to be clinically unstable, or
 - no further tumor assessments are done, or
 - the next timepoint responses are all iUPD, and iCPD never occurs , or
 - if the patient dies from their cancer.

An iUPD assessment followed by subsequent non-PD assessments will not be considered as the start of progression. Stopping protocol treatment due to clinical instability is identified as subjects discontinuing from SOT101 with reason 'clinical progression'.

- Per PCWG3-modified RECIST 1.1: Duration of response is defined as the time from first documentation of overall response leading to a confirmed CR or PR until the time of first documentation of overall response of (confirmed) disease progression (PD) or death.

Clinical deterioration alone will not be considered as documented disease progression. Only tumor assessments performed before or on the start of any new anti-cancer treatment (including radiation therapy to the tumor lesion (s)) will be considered in the assessment of DOR and iDOR.

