10.13.9 Time to Response (TtR and iTtR)

- Per RECIST (v1.1): TtR is defined as the time from the first day of study treatment until the first date of confirmed PR or CR. The date of confirmed response would be the date of the first PR or CR that is confirmed by a later PR or CR.
- Per iRECIST: iTtR is defined as the time from the first day of study treatment until the first date of iPR or iCR. The date of confirmed response would be the date of the first iPR or iCR that is confirmed by a later iPR or iCR.

Time to response is only calculated for patients with measurable disease.

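### An unevaluable (NE) scan after an unconfirmed iRECIST progression can remove or delay the iPFS and iDoR event, because the SAP's fallback rules do not provide for NE

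*SAP*

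**What the plan says.** For iPFS, SAP 10.13.8 sets the base rule: "The date of disease progression would be the date of the first iUPD that is confirmed by a later iCPD". It then lets an unconfirmed iUPD count as progression in four cases:

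- treatment was stopped for clinical instability;
- "no further tumor assessments are done";
- "if the next timepoint responses are all iUPD, and iCPD never occurs";
- the patient died of the cancer.

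SAP 10.13.6 repeats these cases for iDoR. Both sections add that "An iUPD assessment followed by subsequent non-PD assessments will not be considered as the start of progression". Neither mentions NE or defines non-PD.

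The first case is made operational narrowly: "Stopping protocol treatment due to clinical instability is identified as subjects discontinuing from SOT101", with clinical progression as the recorded reason.

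A patient without an event is censored at the last evaluable tumor assessment (SAP 12.7.4 and 12.7.6). An iUPD scan is evaluable, so it can be the censoring date.

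On the response side, iBOR Step 2 in SAP 10.13.3 requires two iPR or iCR determinations "with no other assessment between the two determinations other than NE, iCR, iPR". For iTtR, SAP 10.13.9 asks only for "the date of the first iPR or iCR that is confirmed by a later iPR or iCR" and places no condition on the scans in between.

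**The concern.** The fallback cases are there so that a suspected progression is not lost when the confirming scan never comes. An unreadable confirming scan is an obvious instance of that, and the text leaves it out. A patient whose follow-up scan could not be read is then treated more favorably than one who had no follow-up scan at all, although neither scan history says anything more about the tumor. The censoring falls on or shortly after the scan that raised the suspicion, so it is not independent of prognosis. In RECIST 1.1 PFS the same iUPD is an event, because SAP 10.13.1 maps it to PD.

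Two related gaps affect the same endpoints. Protocol 7.1 lets pembrolizumab continue after SOT101 stops. A patient who stops SOT101 for an adverse event and later stops pembrolizumab for clinical progression is therefore not recognized as a clinical-instability stop. And a patient with iPR, iUPD, iPR can have a time to response under 10.13.9 while being iSD for iBOR and a non-responder for iORR.

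**Working it through.** The plan states no figure that depends on these rules, so there is none to reproduce. The check applies the text literally to scan sequences.

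Inputs: scans every 6 weeks (Protocol 8.1.1.2); event rules from SAP 10.13.6 and 10.13.8; censoring from SAP 12.7.4 and 12.7.6. Assumed: no clinical-progression stop, no death, no new therapy.

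**1. iPFS by sequence** (scans at weeks 6, 12, 18, 24)

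| Sequence | As written | NE ignored |
|---|---|---|
| iSD, iUPD | event, week 12 | event, week 12 |
| iSD, iUPD, iUPD | event, week 12 | event, week 12 |
| iSD, iUPD, NE | censored, week 12 | event, week 12 |
| iSD, iUPD, iUPD, NE | censored, week 18 | event, week 12 |
| iSD, iUPD, NE, iUPD | event, week 24 | event, week 12 |
| iSD, iUPD, NE, iCPD | event, week 12 | event, week 12 |
| iSD, iUPD, NE, iSD | censored, week 24 | censored, week 24 |

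In row 3 a further assessment was done and the later responses are not all iUPD, so no case applies. In row 5 the first iUPD fails for the same reason, but the second is followed by no scan and so is an event: 24 − 12 = 12 weeks late.

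**2. iDoR.** Take iPR, iPR, iUPD, NE at weeks 6, 12, 18, 24. The response is confirmed and dated week 6. The duration is 18 − 6 = 12 weeks either way, but censored as written and an event if NE is ignored.

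**3. How general the effect is.** Take every sequence of 1, 2 or 3 scans after a first iUPD, drawn from NE, iUPD, iCPD and iSD, with iCPD only as the last scan. Keep those that contain an NE and would be events if NE were ignored.

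| Scans after iUPD | Sequences | Event removed | Event delayed | Unchanged |
|---|---|---|---|---|
| 1 | 1 | 1 | 0 | 0 |
| 2 | 4 | 2 | 1 | 1 |
| 3 | 13 | 5 | 3 | 5 |

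For two scans: NE-NE and iUPD-NE remove the event, NE-iUPD delays it, NE-iCPD leaves it. These are counts of patterns, not patient frequencies. Every change goes one way: the event is lost or later.

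**4. Scale of one patient.** A Kaplan-Meier step for one event is S(t−)/n. With no earlier censoring, S(t−) = n/N, so the step is 1/N. The smallest planned futility sample gives 1/12 = 8.3 percentage points and the largest planned cohort 1/57 = 1.8 points, at that date. Cohort sizes actually reached are not in the documents.

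**5. Response side.** iPR, NE, iPR gives iBOR iPR. iPR, iUPD, iPR gives iBOR iSD, yet the later iPR satisfies the iTtR sentence. iPR, iSD, iPR behaves the same way, so the mismatch is not specific to iUPD.

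**The case against.** The best defense is that the text is silent rather than wrong: the second case could mean no further evaluable assessments, since the censoring tables speak of evaluable and adequate assessments. That would settle a single trailing NE. But SAP 10.7 treats non-evaluable scans as tumor assessments, SAP 12.7.6 writes evaluable where it means it, and SAP 10.13.3 names NE where NE is to be neutral. It would also leave iUPD, iUPD, NE and iUPD, NE, iUPD unsettled for the first iUPD. Non-PD could even be read to include NE, so that an unreadable scan resolves the iUPD. SAP 10.13.2 lists Non-PD and NE as separate bone-scan results, which argues against that reading but does not exclude it here. Two programmers could produce different iPFS data.

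Other parts of the defense stand, and limit what may be inferred:

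- *NE always cancels a progression.* It does not. A later iCPD, a clinical-progression stop of SOT101 or a cancer death keeps the iUPD date. Other deaths remain events at the date of death, subject to the missed-assessment rule.
- *NE favors the treatment on both sides.* It does not. The examples in SAP 10.13.3 show that a PR followed only by NE is not a confirmed response. NE is harmless only between two responses.
- *iORR is biased downward because a resolved iUPD breaks confirmation.* This is not generally so. Protocol 10.2.6 says "the initial iUPD is considered to be pseudoprogression", but the iBOR window runs to confirmed progression, so iUPD, iPR, iPR and iPR, iUPD, iPR, iPR both count as responses. An iSD between two iPRs also blocks confirmation. The iBOR rule is thus a strict but coherent choice, and admitting iUPD while still refusing iSD would create a new anomaly.

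The stop-reason point is small. Once NE is handled, it can matter only where a later scan is stable or better, and there the SAP does not say which rule prevails.

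**Conclusion.** The gap is real and worth closing. As written, an iUPD followed only by NE, or by further iUPD and then a final NE, is censored for iPFS and iDoR when there is no clinical-progression stop of SOT101 and no death. With no later scan it would be an event at the iUPD date. iUPD, NE, iUPD is still an event, but dated at the second iUPD.

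Per affected patient this is an event turned into a censoring, or an event 12 weeks late in the sequence worked above. How many patients are affected cannot be derived from the documents. The conclusion rests on the literal reading, which the SAP's own usage elsewhere supports.

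The reach is limited to secondary, descriptive endpoints. These are still to be reported: SAP 6.1 drops only the exploratory endpoints after recruitment stopped. The primary ORR is untouched, because RECIST 1.1 response is not derived after the first iUPD (SAP 10.13.1). The iTtR mismatch with iBOR and iORR is a separate wording gap, to be closed on the iTtR side.

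**What to change.** In SAP 10.13.6 and 10.13.8:

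- insert the word evaluable in the second fallback case, so that trailing NE scans count as no further assessment;
- in the third case, let the later responses be iUPD or NE, still with iCPD never occurring;
- replace non-PD in the resolution sentence by iSD, iPR, iCR or Non-iCR/Non-iUPD;
- take the clinical-progression stop reason from the last study drug discontinued instead of SOT101 alone.

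In SAP 10.13.9, state that a confirmed response for TtR and iTtR is one confirmed under 10.13.3. iPR, iUPD, iPR is then handled alike in iTtR, iBOR and iORR. Leave iBOR Steps 1 to 3 as they are.

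The cost is SAP text and programming; no new data are needed. The results may show a few more, or earlier, iPFS and iDoR events. The change should be dated before database lock. If lock has passed, run the revised rules as a labeled sensitivity analysis and report how many patients change status.

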### 9.3 Statistical analyses

#### 9.3.1 General considerations

Analyses will be descriptive (i.e., without a comparison). Efficacy analyses will be performed for each indication separately. Safety will be analyzed as described in section [9.3.3](#).

Summary statistics will include:

- Counts and percentages (categorical data)
- Number of observations, mean, standard deviation, median, minimum, and maximum (continuous data)

The ORR, iORR, BOR, iBOR, CBR, iCBR, CTC response, and PSA response will use the exact method based on the binomial distribution[56](#) to derive 95% confidence intervals (CIs).

---

Kaplan-Meier estimations and estimations of median (if reached) with log-log 95% CI, Q1 (25th percentile), and Q3 (75th percentile) will be used for time to confirmed PSA progression (mCRPC only), DoR, iDoR, PFS, iPFS, TtR, iTtR, and OS. In case of a confirmed response or disease progression, the date of the first tumor assessment or PSA evaluated as response or progression will be used for the time-to-event variables.

Depending on the amount of missing data, a sensitivity analysis will be performed for time-to-event endpoints. If such an analysis is planned, it will be described in the final Statistical Analysis Plan (SAP).

The last value of PSA, CTC count, CT scan, bone scan, or MRI on or up to 28 days before the date of the first study treatment will be used as the baseline value for each assessment. Only tumor assessments prior to or at the date of initiation of further-line therapy and using CT scan, bone scan, or MRI will be used for the evaluation of tumor response.

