6.1 Changes from Protocol

The following changes to the protocol have been applied:

Endpoint of “Circulating tumor cell (CTC) count conversion from >5 to <5 cells per 7.5 mL of blood” for metastatic castration-resistant prostate cancer (mCRPC) only will be analyzed as a conversion from ≥ 5 to <5 cells per 7.5 mL of blood.

Endpoint of “Confirmed PSA decline of $\geq 50\%$ ” will not only evaluate the response at 6 months post-trial entry: all timepoints will be considered as per the schedule of assessments (Section 1.3.3 of Study Protocol).

Additional sensitivity analyses and exploratory endpoints:

As a sensitivity analysis for Best Overall Response (BOR) as per RECIST 1.1: BOR will also be performed as per Prostate Cancer Clinical Trials Working Group 3 (PCWG3)-modified RECIST 1.1 to study the effect of progressive disease in bone on the BOR, for patients with mCRPC.

As a sensitivity analysis to Clinical Benefit Rate (CBR) as per RECIST 1.1: CBR will also be performed for all patients in mCRPC – with both measurable and non-measurable disease – as per PCWG3-modified RECIST 1.1, to study the effect of progressive disease in bone on the CBR.

Other sensitivity analyses using All Subjects as Treated (ASaT) population on selected efficacy endpoints.

As per the EMA guideline on the evaluation of anticancer medicinal products in man, the endpoint PFS2 has been added as an exploratory endpoint.

Following Futility Analysis in August 2023, recruitment to the study was stopped. Exploratory Endpoints will no longer be analyzed.

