12.7.4 DOR and iDOR

DOR/iDOR will be summarized using Kaplan-Meier estimates for each indication separately. Log-log 95% confidence intervals for estimates of the percentiles will be presented.

Responders will be considered to have an ongoing response if they: i) have not progressed, and ii) have not started a new anti-cancer therapy, and iii) have not been lost to follow-up, and iv) are alive.

Patients with missing data will be censored/considered as having an event as specified below:

Situation	Date of progression or censoring	Outcome
No progression, no death. No start of new anti-cancer therapy.	Date of the last evaluable tumor assessment.	Censored
No progression, no death. Start of new anti-cancer therapy.	Date of the last tumor assessment with non-progression before the start of new anti-cancer therapy.	Censored

Situation	Date of progression or censoring	Outcome
Progression or death after one missed adequate tumor assessment.	Date of progression or death, whichever is earliest (if both occur).	Progressed
Progression or death after more than one (consecutively) missed adequate tumor assessments.	Date of the last evaluable tumor assessment.	Censored

DOR will be calculated based on RECIST 1.1, iRECIST, and PCWG3-modified RECIST for the mCRPC cohort only for those patients with measurable disease at baseline.

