12.7.6 PFS and iPFS

PFS/iPFS will be summarized using Kaplan-Meier estimates for each indication separately. A sensitivity analysis will be performed using the ASaT population.

PFS will be calculated based on PCWG3-modified RECIST for the mCRPC cohort for those patients with both measurable and non-measurable disease.

Patients with missing data will be censored/considered as having an event as specified below:

Situation	Date of progression or censoring	Outcome
Incomplete or no baseline tumor assessments.	Date of the first day of study treatment	Censored
Start of new anti-cancer therapy.	Date of the last tumor assessment with non-progression before the start of new anti-cancer therapy.	Censored
Death before the first disease progression assessment.	Date of death.	Progressed

Situation	Date of progression or censoring	Outcome
Death between adequate tumor assessment visits.	Date of death.	Progressed
Progression or death after one (consecutively) missed adequate tumor assessment ^a .	Date of progression or death, whichever is earliest (if both occur).	Progressed
Progression or death after more than one (consecutively) missed adequate tumor assessments.	Date of the last evaluable tumor assessment.	Censored
No progression, no death.	Date of the last evaluable tumor assessment, or first date of study treatment if no post-baseline tumor assessments.	Censored

^aIdentified as 12 weeks between the date of last evaluable tumor assessment and the date of the event.

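### A progression scan on the day new anti-cancer treatment starts counts for DOR but is dropped for PFS, an inconsistency within the SAP

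*SAP*

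**What the plan says.** Two parallel sentences in the SAP set the cut-off for usable scans once a patient moves to another treatment, which in both places includes radiotherapy to tumor lesions. SAP 10.13.6 (DOR and iDOR) uses "Only tumor assessments performed before or on the start of any new anti-cancer treatment". SAP 10.13.8 (PFS and iPFS) uses "Only tumor assessments performed before the start of any new anti-cancer treatment".

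The censoring tables differ as well. In SAP 12.7.4 the DOR row applies to "No progression, no death. Start of new anti-cancer therapy", so it cannot catch a patient who has progressed. In SAP 12.7.6 the PFS row is labelled only by the start of new therapy, with no such condition, and sets the censoring date as "Date of the last tumor assessment with non-progression before the start of new anti-cancer therapy".

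Protocol 9.3.1 gives a general rule for evaluating tumor response: "Only tumor assessments prior to or at the date of initiation of further-line therapy". The PFS table in Protocol 9.3.3.2 has the same unconditioned row as SAP 12.7.6. SAP 6.1, which opens "The following changes to the protocol have been applied", does not mention a different cut-off for PFS.

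**The concern.** When a scan shows progression and the next treatment starts that day, the scan may well be the reason for the switch. Under the DOR rule it is an event. Under the PFS rule it does not exist, and the patient is treated as progression-free at the scan before it. Censoring caused by the progression itself is informative, which is what Kaplan-Meier estimation assumes away. In a responder the two endpoints would also contradict each other: a response that ended in progression, in a patient whose PFS record shows none.

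Nothing in the SAP suggests that the difference is deliberate. A programmer following the text would have to code two different comparison operators for what looks like one rule.

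**Working it through.** The plan gives no figure for this point, so the check sets the rules side by side and traces one patient through them.

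**Rules compared**

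| | DOR / iDOR | PFS / iPFS |
|---|---|---|
| Scan cut-off | before or on start of new treatment (SAP 10.13.6) | before start only (SAP 10.13.8) |
| New-therapy censoring row | only if no progression and no death (SAP 12.7.4) | no such condition (SAP 12.7.6) |
| Same-day progression scan | event | not considered; censored at previous non-progression scan |

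**One hypothetical patient** (all study days are assumptions): PR on day 43, PR again on day 85, progression scan on day 127, new therapy started on day 127.

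1. Confirmation: 85 − 43 = 42 days, more than the 4 weeks required in SAP 10.13.3, so the patient is a confirmed responder.
2. DOR: the day-127 scan is on the start date and is admitted. The censoring row does not apply because there is progression. DOR is an event, 127 − 43 = 84 days after first response (85 if both days are counted).
3. PFS: the day-127 scan is not before the start date and is left out. The new-therapy row applies, and the last non-progression scan before the start is day 85. PFS is censored at day 85.
4. Gap: 127 − 85 = 42 days between the PFS censoring date and the progression recorded for DOR.
5. With *before or on* in 10.13.8 and a conditioned row in 12.7.6, PFS becomes an event at day 127 and agrees with DOR.

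In a patient without a confirmed response there is no DOR to contradict, and the effect is simply a PFS event lost to censoring. Under iRECIST, a same-day iUPD is an iDOR event only through one of the listed routes, for example "no further tumor assessments are done, or".

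**How ties can arise from imputation.** SAP 10.16.1 replaces a missing day in the start date of follow-up therapy with the first of the month, and pulls a start date imputed later than last contact back to last contact. Under SAP 10.13.15, tumor assessment dates feed the last-contact date. Example (assumed dates): a progression scan on 20 March is the last contact, and new therapy is recorded only as April. The start is imputed as 1 April and then reset to 20 March. A scan that truly preceded treatment is now on the start date, so it is kept for DOR and dropped for PFS.

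**Effect on the PFS curve.** Take three patients: the one above, and two others with events at days 100 and 200.

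- Index patient has an event at day 127: S(100) = 2/3; S(127) = 2/3 × 1/2 = 1/3.
- Index patient is censored at day 85: two remain at risk at day 100, so S(100) = 1/2, and S(127) = 1/2.

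The dropped event lowers the curve from day 100 to day 127 (1/2 against 2/3) and raises it from day 127 until the last event at day 200 (1/2 against 1/3).

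**The case against.** The strongest reply is that this is a rare tie on a secondary endpoint in a descriptive study. Most of that stands. Protocol 8.1.1.2 and 10.2.2 keep clinically stable patients on treatment after first progression until a repeat scan, 4 to 8 weeks later under 8.1.1.2. RECIST 1.1 PFS is dated at the first progression, so new therapy will usually start well after that scan. The clash with DOR also needs a confirmed responder.

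Several stronger readings are tempting, and the documents do not support them:

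- *That the SAP departs from the protocol's PFS rule.* Protocol 9.3.1 speaks of evaluating tumor response and does not name PFS. The protocol's own PFS table contains the same unconditioned row, with a censoring date before the start of therapy. The protocol is not clear enough on PFS for the silence of SAP 6.1 to count as an undeclared change.
- *That the effect always flatters PFS.* The three-patient example shows that it can lower the curve between the censoring date and the true event date. Only the later part is generally raised.
- *That a number of lost events per cohort can be stated.* If one assumed that 2% to 5% of 40 progressors were affected, the result would be 0.8 to 2 events. Neither input is in the documents, and since recruitment stopped after the August 2023 futility analysis (SAP 6.1), 40 progressors per cohort is doubtful.
- *That the unconditioned row censors everyone who moves on to new therapy, even after earlier progression.* SAP 10.13.8 admits scans before the start and defines PFS by the first radiological progression, so earlier progression remains an event.

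One could also read *before* by clock time, so that a morning scan precedes an afternoon infusion. The SAP does not say so, and the explicit *or on* in 10.13.6 argues against it.

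**Conclusion.** The inconsistency is real and sits in the current text of SAP 10.13.6 and 10.13.8, reinforced by the differing rows in 12.7.4 and 12.7.6. As written, a progression scan on the start date of new treatment is a DOR event in a confirmed responder and a PFS censoring in the same patient. In a non-responder it is a lost PFS event.

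Severity is minor. How many patients are affected cannot be derived and is probably few. The 42-day gap in the example rests on assumed visits at the nominal 6-week scan interval; with the ±2-week windows it could be shorter or longer. PFS is secondary and only described. ORR, the ORR-based futility rules and the sample size do not depend on it. The point is worth making because it removes an avoidable loss of documented events to informative censoring at almost no cost.

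**What to change.** In SAP 10.13.8, change *before* to *before or on*, matching 10.13.6. In the new-therapy row of SAP 12.7.6, add the condition that no progression was documented on or before the start date. Because the row in Protocol 9.3.3.2 has no such condition, one line in SAP 6.1 should record the clarification. If the difference between DOR and PFS is in fact intended, it should be stated and justified there instead.

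SAP 10.13.3 and 10.13.5 need no change: their wording does not conflict with either rule.

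The cost is a short SAP edit and one comparison operator in the PFS program. No new data are needed.
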